Community Observer. During the screening or treatment visit, participants will be asked to provide the name and contact information (phone number and email address; email will be the preferred method of contact) for a family member, friend, roommate, or significant other for the purposes of online surveys about their caffeine use. The participant will be asked to confirm with their observer that the study team has permission to contact them. The observer will be contacted twice to complete a brief online survey regarding the participants' caffeine use. The first contact will occur soon after the participant has the *Treatment* visit. The second contact will occur near the time of the participant's *Week 7 follow-up* visit.

Treatment Televisit. Participants determined to be eligible following the screening televisit will be scheduled to complete the treatment televisit shortly after screening. For the immediate treatment group, the treatment the *Treatment* visit will generally occur within one week of the screening televisit. The delayed treatment group will have their *Treatment* visit scheduled for a date approximately 7 weeks after screening. During the *Treatment* televisit, study staff will provide the participants with a digital copy of the caffeine reduction treatment manual used in prior studies (Evatt et al., 2016; Sweeney et al., 2019). As in prior research (Sweeney et al., 2019), study staff will give a brief (i.e., generally less than five minutes) description of the manual and instructions on how to gradually reduce their caffeine consumption over a period of six weeks. Participants will also complete assessments to determine their caffeine consumption and cigarette use over the past 7 days as outlined in Table 1. Participants will also be provided with information about their follow-up visits and how to complete weekly surveys.

Weekly Surveys. At seven days following the treatment televisit, participants will receive a request to complete a survey via Qualtrics link sent via email/text. The survey will consist of standard assessments of anxiety, depressed mood, sleep problems, gastrointestinal problems, past week caffeine/cigarette intake, and problems related to caffeine as outlined in Table 1. They will receive a request to complete the same survey once per week (weeks 1-6) until the Week 7 follow-up televisit.

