Week 7 Follow-up Televisit. At approximately 7 weeks after the treatment televisit, participants will complete a follow-up televisit at which they will complete the same measures as previously administered to assess anxiety, depressed mood, sleep problems, gastrointestinal problems, past week caffeine/cigarette use, and caffeine-related problems as outlined in Table 1. Participants will also complete a treatment acceptability survey.

Week 14 Follow-up Televisit. Finally, participants will complete a follow-up visit approximately 14 weeks after the treatment televisit. They will complete all the same assessments as the Week 7 televisit, except they will not repeat the treatment acceptability survey.

Table 1. Study measures according to visit

	Preliminary Online Screening	Screening Televisit	Treatment Televisit	Weekly Surveys (Weeks 1-6)	Week 7 Televisit	Week 14 Televisit
Basic screening questions/demographics ¹	X					
Typical Week Caffeine Survey	X					
AUDIT-C ²	X					
DAST-10 ³	X					
PROMIS-Anxiety-8a ⁴	X			X	X	X
PROMIS-SleepDisturbance-8a ⁴	X			X	X	X
PROMIS-GIDiarrhea-6a ⁴	X			X	X	X
PROMIS-GIReflux-13a1.0 ⁴	X			X	X	X
PROMIS-Depression-8a ⁴	X			X	X	X
Consent Quiz ¹		X				
Medical History Survey ¹		X				
Drug Use History Matrix ¹		X				
Caffeine Timeline Follow-back ¹		X	X		X	X
Past 7 Days Caffeine Survey ¹		X	X	X	X	X
Past 7 Days Cigarette Survey (smokers only) ¹		X	X	X	X	X
Caffeine Problems Survey ¹		X				
Caffeine Use Disorder Questionnaire ¹		X			X	X
Caffeine Use Disorder Interview ¹		X				
GAD-7 ⁵		X			X	X
PSQ-I ⁶		X			X	X
Insomnia Severity Index ⁷		X			X	X
GSRS ⁸		X			X	X
Treatment Acceptability Survey/Interview ¹					X	
Observer Rating Survey (Completed by Community Observer) ¹				X		X

Note. Detailed descriptions of all measures are appended to the present IRB application in the "Measures" document. ¹Study team-generated measure/survey based on prior research (e.g., Sweeney et al. 2019, 2020). ²Alcohol Use Disorders Identification Test-C, Bush et al., 1998. ³Drug Abuse Screening Test, Skinner 1982. ⁴Patient-Reported Outcomes Measurement Information System, Cella et al., 2010, Rothrock et al., 2010. ⁵Generalized Anxiety Disorder-7, Spitzer et al., 2006. ⁶Pittsburgh Sleep Quality Index, Buysse et al., 1989. ⁷Bastien et al., 2001. ⁸Gastrointestinal Symptom Rating Scale, Svedlund et al., 1988.

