There will be no anticipated disruption to any ongoing treatment or routine care.

- f. Justification for inclusion of a placebo or non-treatment group.

There will be no anticipated placebo or non-treatment group. These are pilot or preliminary data that may support a future randomized trial which would have a separate IRB approval.

- g. Definition of treatment failure or participant removal criteria.

Participants who are not eligible or who are noncompliant with study tasks will be removed from the study early. There are no other early stopping rules in the study.

- h. Description of what happens to participants receiving therapy when study ends or if a participant's participation in the study ends prematurely.

The intervention consists solely of the treatment manual and brief instructions provided at the treatment televisit, and is not accompanied by any ongoing therapy (Sweeney et al., 2019). All participants who complete the treatment televisit will be able to keep their copy of the treatment manual.

5. Inclusion/Exclusion Criteria

Inclusion Criteria

1. Between 18-75 years old
2. Reside in the United States
3. Read, write, and speak English fluently
4. Able to access a video camera on a smartphone, tablet, or other computer
5. Able to receive text messages or emails (or both)
6. Consume greater than or equal to 200 mg caffeine per day in a typical week
7. Indicate a problem that is caused or worsened by caffeine from among the following options: sleep problems, anxiety or nervousness, frequent urination, heartburn or other digestive issues, feel dependent on or addicted to caffeine

8. Interested in getting help to gradually reduce or eliminate caffeine consumption as part of a research study

Exclusion Criteria

1. Evidence of significant depressive symptoms assessed via PROMIS-Depression-8a and medical history
2. Evidence of problematic alcohol use assessed via the AUDIT-C and medical/substance use history
3. Evidence of problematic substance use other than alcohol, nicotine, or caffeine assessed via the DAST-10 and medical/substance use history
4. Evidence of a significant psychiatric disorder, presentation of acute psychiatric symptoms, or any other mental illness that, in the opinion of the investigators, may complicate participation in the study. [Anxiety and sleep disorders are not anticipated to interfere with study participation and will not generally be exclusionary]

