5. Any medical condition that, in the opinion of the investigators, may interfere with or preclude completion of the study

6. Drugs/ Substances/ Devices

- a. The rationale for choosing the drug and dose or for choosing the device to be used.

There are no proposed drugs or devices in the proposed research study.

- b. Justification and safety information if FDA approved drugs will be administered for non-FDA approved indications or if doses or routes of administration or participant populations are changed.

N/A

- c. Justification and safety information if non-FDA approved drugs without an IND will be administered.

N/A

7. Study Statistics

- a. Primary outcome variable.

To determine to what extent participants will engage with a remote caffeine reduction intervention for caffeine-related problems and find it acceptable (*Primary objective*), we will calculate the percentage of completed assessments for each televisit (Treatment, 7 Week Follow-Up, 14 Week Follow-Up) among eligible participants, as well as self-reported agreement with the items on the treatment acceptability survey completed at the 7 Week Follow-Up televisit (e.g., “I read all or most of the Guide to Caffeine Reduction and Cessation,” “Overall, the guide was helpful during my attempt to reduce or quit caffeine.”)

- b. Secondary outcome variables.

To determine to what extent participants are successfully able to reduce their caffeine consumption following the remote intervention (*Secondary objective (a)*), we will assess caffeine consumption as determined by the caffeine surveys at 7-and 14-week post-treatment follow-ups and compare this with consumption at the screening and treatment televisits.

To determine to what extent participants report improvement in common caffeine-related problems (e.g., insomnia, anxiety, gastrointestinal distress) following the remote intervention (*Secondary objective (b)*), we will assess caffeine related problems, anxiety, sleep problems, and gastrointestinal distress via standardized measures (see Table 1) at 7 and 14 weeks post treatment follow-ups and compare this with scores on these assessments at the screening and treatment televisits.

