To determine whether participants randomized to the immediate intervention group show greater caffeine reductions or greater improvements in caffeine-related problems (*Secondary objective (c)*) at the 7-week follow-up relative to the delayed treatment group over the same time-period, we will compare all of the secondary outcome variables described above between the two treatment groups to compare our intervention relative to spontaneous reduction that may occur with the passage of time.

c. Statistical plan including sample size justification and interim data analysis.

Because the primary purpose of this study is to collect pilot and feasibility data rather than determine efficacy via randomized controlled trial, the statistical analysis will be primarily descriptive. Primary outcomes will be reported as the proportion of completed televisits among eligible participants as well as the mean and standard deviation agreement (visual analog scale) with items on the treatment acceptability survey. With respect to secondary outcomes, means and standard deviations for the standardized assessments in Table 1 will be calculated for screening, treatment, 7 Week Follow-Up and 14-Week Follow-Up visits, and we will also visually inspect individual subject data. With respect to comparisons between the immediate and delayed intervention group, we will use a mixed effects regression model with between-subjects factors of group, a within subjects factor of time, and a group x time interaction term. A power analysis indicates that with two groups, four measurements, an alpha of .05, a desired power of .95, correlation among repeated measures of .5, and conservatively estimating a small effect (e.g., partial eta squared = .02), a sample size of 100 will be sufficient to detect a treatment effect. Further, we will calculate Cohen's *d* and partial eta squared effect sizes using means and standard deviations for pre-and post-treatment for all secondary outcomes. These effect size calculations will be used to determine the necessary sample size for any future large-scale randomized controlled trials to assess clinical effects in different treatment populations. The desired sample size of 100 is also based on our laboratory's proven participant capacity for prior randomized clinical trials and long-term human laboratory studies (e.g., Evatt et al., 2016; Sweeney et al., 2017, Sweeney et al., 2019).

d. Early stopping rules.

8. Risks

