a. Medical risks, listing all procedures, their major and minor risks and expected frequency.

Risks of the study procedures: The procedures employed in this study are benign. There are also no specific risks related to the questionnaire assessments. It is possible that interview questions pertaining to psychological health or other medical history could cause participants to feel uncomfortable. Participants may feel tired, bored or annoyed when responding to surveys. Heavier caffeine users may experience unpleasant withdrawal symptoms when reducing caffeine consumption, though the gradual reduction over a period of weeks was specifically designed to reduce the frequency and severity of withdrawal. Common withdrawal symptoms include headache, tiredness/fatigue, decreased energy/activeness, decreased alertness/attentiveness, drowsiness/sleepiness, decreased contentedness/well-being, depressed mood, difficulty concentrating, irritability, muzzy/foggy/not clearheaded, muscle pain/stiffness, flu-like symptoms, or nausea and/or vomiting (Juliano & Griffiths, 2004). Caffeine withdrawal is a transient phenomenon with little medical risk. There is no evidence to suggest caffeine reduction is contraindicated to pregnancy (and in fact caffeine reduction may be beneficial for pregnant women; Chen et al., 2016).

Thus, pregnant women, breastfeeding women, or women who are not using an effective means of birth control may be included in the study sample.

Risks of a breach in confidentiality: Although we make every attempt to keep participant information and data private and stored in a secure place, there is always a risk that sensitive participant information might be accidentally disclosed to someone outside of the research project.

b. Steps taken to minimize the risks.

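### Depressed mood, a listed withdrawal symptom scored nine times per participant, is not a named outcome in section 7.b and has no 7-week score in the delayed arm

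*Combined protocol and SAP*

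**What the plan says.** Section 7.b defines the secondary outcomes. Objective (a) is caffeine consumption. For objective (b), "we will assess caffeine related problems, anxiety, sleep problems, and gastrointestinal distress via standardized measures (see Table 1". For objective (c), "we will compare all of the secondary outcome variables described above between the two treatment groups". Depressed mood appears in none of these.

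The trial does measure it. The weekly surveys in section 4.a contain "standard assessments of anxiety, depressed mood, sleep problems, gastrointestinal problems", and participants "They will receive a request to complete the same survey once per week (weeks 1-6) until the Week 7 follow-up televisit" (the sentence's subject and verb are part of the quote). Table 1 also marks "PROMIS-Depression-8a" at the preliminary online screen, Week 7 and Week 14. It marks nothing for this scale at the Screening or Treatment televisit.

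Two other places bear on the scale. Section 8.a includes "decreased contentedness/well-being, depressed mood, difficulty concentrating, irritability" among common withdrawal symptoms. The first exclusion criterion in section 5 is "Evidence of significant depressive symptoms assessed via PROMIS-Depression-8a and medical history".

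Section 7.c promises means and standard deviations of the standardized Table 1 assessments at four visits, a mixed model for the group comparison, and effect sizes for all secondary outcomes.

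**The concern.** Section 7.b frames every symptom outcome as improvement and names none as a possible harm. Depressed mood is a harm that the protocol itself lists and already scores on a standard scale, but no between-arm estimate of it is planned.

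What remains is a set of visit means without a control. If the Week 7 mean is above the entry mean, the rise could come from caffeine reduction or from having excluded high scorers at entry, and the planned summaries could not separate the two. This matters because the pilot's effect sizes are meant to inform the size of later trials, and because the intervention is a manual with brief instructions and no ongoing therapy.

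**Working it through.** **1. Count of administrations (Table 1; section 4.a, Weekly Surveys).** Preliminary screen 1 + weekly surveys 6 + Week 7 1 + Week 14 1 = 9. One falls before treatment and eight after.

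**2. Sections 7.b and 7.c side by side.** Section 7.b lists consumption, caffeine-related problems, anxiety, sleep and gastrointestinal distress. The randomised comparison is tied to that list. Section 7.c introduces the Table 1 means under the heading of secondary outcomes, which could be read as bringing depression in. The same reading would bring in AUDIT-C and DAST-10, which are given only at screening, so the phrase does not work as an outcome definition. The weekly scores fall outside the four visits that 7.c names; apart from visual inspection of individual data, no analysis is stated for them.

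**3. Is a randomised 7-week contrast possible as scheduled?** The delayed arm's 7-week pre-treatment point is its Treatment televisit. Table 1 and section 4.a give that visit only caffeine and cigarette measures. Depression has no score there, and neither do the anxiety, sleep, gastrointestinal or caffeine-problem scales. Section 7.b nonetheless speaks of comparing follow-up with scores at the screening and treatment televisits. As scheduled, no symptom scale has a delayed-arm value at 7 weeks.

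**4. The plan's own sample-size figure.** Inputs from 7.c: two groups, four measurements, alpha .05, correlation .5, partial eta squared .02, N = 100. For the group-by-time test, f² = .02/.98 = 0.0204, noncentrality = 0.0204 × 100 × 4/(1 − .5) = 16.3, and degrees of freedom are 3 and 294. Power is 0.936 against the stated .95, which is close enough to count as reproduced. Naming depressed mood in 7.b changes none of these figures.

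**5. Drift of the uncontrolled change.** The protocol gives neither a cut-off nor a retest correlation, so both are assumed: exclusion above a cut c of 0.5 to 1.5 SD over the mean, and r from .5 to .8. For a normal score sharply truncated at c, expected drift with no effect = (1 − r) × φ(c)/Φ(c).

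| c | r | Drift (SD) |
|---|---|---|
| 0.5 | .5 | 0.255 |
| 1.0 | .7 | 0.086 |
| 1.5 | .8 | 0.028 |

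Both arms pass the same screen before randomisation, so drift common to them cancels in a between-arm contrast of change.

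**6. Precision of that contrast.** Assume 50 per arm (100 split equally), r = .5 as in 7.c, and full retention. Half-width of the 95% interval = 1.96 × √[2(1 − .5) × 2/50] = 1.96 × 0.20 = 0.39 SD.

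**7. Timing.** Section 8.a calls withdrawal transient, and the reduction runs over six weeks. A Week 7 contrast therefore bounds persistent worsening only. Any earlier worsening would show in the weekly scores, but those start after the treatment visit, so the delayed arm has none while waiting and they cannot be compared between arms.

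**The case against.** The strongest reply is that nothing has been singled out for omission. A reader might infer that the trial yields randomised estimates of the benefits and withholds one for a harm. Step 3 shows otherwise: the missing 7-week assessment is shared by all the symptom scales. This stands, and it means the schedule change should not be made for depression alone.

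A reader might also infer that only symptoms expected to improve are compared. That too goes beyond the documents. Consumption is compared as well, and the withdrawal list includes drowsiness and nausea, so scores in the sleep and gastrointestinal domains could worsen.

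Nor can it be said flatly that the effect sizes exclude depression, since the wording of 7.c leaves room to include it. That ambiguity is a reason to reconcile 7.b with 7.c. It does not supply a controlled estimate.

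The drift argument rests on assumptions. Exclusion uses the scale together with medical history, no cut-off is stated, and the low end of the range is negligible. Scores may drift upward; the documents do not establish that they will.

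Finally, this is a mainly descriptive pilot whose objective (b) concerns improvement, and adverse events are reported under a separate monitoring plan. That limits the weight of the point. Adverse-event reports, however, do not give a between-arm difference on a scale.

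**Conclusion.** The point holds in limited form. Depressed mood is collected nine times and listed as a withdrawal symptom, but it is not named in 7.b. At most it would be reported as uncontrolled visit means, judged against a single pre-treatment score that also served for exclusion. Change from that score could be off by about 0.03 to 0.26 SD, under sharp truncation at 0.5 to 1.5 SD and retest correlations of .5 to .8.

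A between-arm contrast would remove the common part of that drift and give an interval of about ±0.39 SD, assuming 50 per arm, r = .5 and no dropout; loss to follow-up would widen it. The contrast needs a delayed-arm score that is not now collected, and it speaks to persistent worsening only. The documents do not support a charge of selective reporting.

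**What to change.** - In 7.b, name depressed mood (PROMIS-Depression-8a) as a possible-harm outcome under objectives (b) and (c), and align the wording of 7.c with that list.
- In Table 1 and section 4.a, add the form at the Treatment televisit. The anxiety, sleep, gastrointestinal and caffeine-problem scales have the same gap and need the same addition if objective (c) is to be answered for them. In both arms this also gives a pre-treatment depression score that was not used for exclusion.
- In 7.c, report the 7-week between-arm difference in depressed mood with a 95% interval, and include the scale in the effect sizes.
- Summarise the depression scores for weeks 1–6 descriptively, noting that the waiting arm has no counterpart.

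For depression the cost is eight more items at an existing visit, some added text in 7.b and 7.c, one more model fit and a simple weekly summary; the other scales would add items of their own. The downside is one more secondary estimate, to be reported with its interval and not as a test of benefit. The stated sample size does not change.

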There will be no in-person visits for the proposed study. Study interactions will be conducted entirely remotely via JHMI-credentialed Qualtrics surveys, HIPAA-compliant Zoom meetings created by study staff (i.e., using the JHMI HIPAA-compliant instance), or through other approved Johns Hopkins Telemedicine Services (e.g., Polycom). The present study will consist of a *preliminary online screening* (via JHMI-credentialed Qualtrics survey), followed by a more detailed screening televisit for those individuals who meet preliminary screening criteria. Individuals determined to be eligible following the screening televisit will complete three additional televisits: *Treatment*, *Week 7 follow-up*, and *Week 14 follow-up*. Participants will provide contact information for a community observer who will complete two online surveys, one near the *Treatment* visit and one near the *Week 7 follow-up*. Between the treatment visit and the Week 7 follow-up, participants will complete online surveys once per week. In Table 1 below, we provide a summary of the assessments to be administered at each study time point. Detailed measures and descriptions are also appended to the current application in the "Measures" document.

Preliminary Screening. We have created a preliminary screening survey assessing basic demographics and initial eligibility via JHMI-credentialed Qualtrics survey. Links to the survey will be provided via online or paper flyer advertisements (e.g., Psychiatry department website, Google/Facebook ads) or in response to email/telephone inquiry. Individuals who complete the preliminary screening and indicate interest in participation will provide their first name and telephone number as part of the survey. Individuals who meet initial eligibility criteria will be contacted via phone to determine a time for the screening televisit and to receive instructions.

Screening Televisit. Study staff will create a HIPAA-compliant Zoom meeting with the participant, or using other approved Johns Hopkins Telemedicine Services (e.g., Polycom) in the event of technical or other issues with Zoom. The visits will be password-protected and will require the participant to use video

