during the call. Study staff will also use video whenever possible. The study staff will use the Zoom chat function or email to send the participant survey links and will verbally instruct them on how to complete the surveys, beginning with the consent survey. The oral consent form document will be embedded within the Qualtrics survey such that the participant can download the consent form document, or alternatively may be emailed to the participant. The study staff will ask the participant to read aloud the first part of the consent form in order to confirm that they were able to download the document and are able to read English fluently. Then the participant will be provided the opportunity to review the document and ask the study staff any questions they have about participation. This will be followed by a consent quiz administered via Qualtrics survey link. Participants will provide oral consent and answer all of the consent quiz questions correctly prior to proceeding with the remaining screening questionnaires. Following consent, participants will complete standardized medical/substance use history questionnaires as well as surveys to determine their caffeine/cigarette use, caffeine-related problems, and standardized assessments of anxiety, sleep, and gastrointestinal problems as outlined in Table 1. The participant will fill out the surveys via Qualtrics links, or the study staff will interview them and enter their responses on the study staff computers. Study staff will provide instructions to guide them through the assessment completions, review their responses on Qualtrics, and may ask follow-up questions if necessary, to supplement their survey responses. After determining eligibility, participants will be randomized to either the Immediate or Delayed treatment group using an urn randomization procedure accounting for caffeine consumption, age, and sex as was utilized in prior research in our laboratory (Evatt et al., 2016; Sweeney et al., 2019).

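### Table 1 gives the five PROMIS scales at neither pre-treatment televisit named in 7.b, and no PROMIS baseline is designated; the harm falls mainly on depressed mood

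*Combined protocol and SAP*

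**What the plan says.** Section 7.b (secondary objective b) measures caffeine-related problems, anxiety, sleep and gastrointestinal distress at Weeks 7 and 14 after treatment and will "compare this with scores on these assessments at the screening and treatment televisits". It names no instrument and refers to Table 1. Section 7.c plans means and standard deviations of the Table 1 standardised assessments at screening, treatment, Week 7 and Week 14. It also plans pre-post effect sizes for the secondary outcomes, to be used in sizing future trials.

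Table 1 marks all five PROMIS forms (Anxiety, Sleep Disturbance, GI Diarrhea, GI Reflux, Depression) at Preliminary Online Screening, Weekly Surveys, Week 7 and Week 14. The Screening and Treatment televisit columns are blank in these rows.

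Section 4.a describes the online instrument as a "preliminary screening survey assessing basic demographics and initial eligibility via JHMI-credentialed Qualtrics survey". Consent comes later, at the Screening televisit: "Participants will provide oral consent and answer all of the consent quiz questions correctly prior to proceeding with the remaining screening questionnaires". Exclusion criterion 1 reads: "Evidence of significant depressive symptoms assessed via PROMIS-Depression-8a and medical history".

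**The concern.** A comparison with the Screening and Treatment televisits needs a score from at least one of them, and PROMIS has none. An analyst would have to fall back on the online form, which the plan does not call a baseline and whose age at randomisation is not limited.

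For PROMIS-Depression there is a further problem. People who score high on the form can be excluded because of that score. Those who remain have, on average, online scores below their usual level, and later scores drift back up with no real change in mood. Section 8.a lists depressed mood as a withdrawal symptom, so such a rise could be misread as an effect of caffeine reduction. No other scale in Table 1 is dedicated to depressed mood, so nothing in the plan would correct that reading.

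**Working it through.** **Step 1: visits planned against visits scheduled.** Sections 7.b and 7.c against Table 1:

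| Measure | Screening televisit | Treatment televisit | Week 7 | Week 14 |
|---|---|---|---|---|
| Five PROMIS forms | no | no | yes | yes |
| GAD-7, Pittsburgh sleep index, Insomnia Severity Index, GSRS | yes | no | yes | yes |
| Past 7 Days Caffeine Survey, Caffeine Timeline Follow-back | yes | yes | yes | yes |

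PROMIS has 0 of 2 pre-treatment televisit values, the other symptom scales have 1 of 2, and caffeine intake has 2 of 2.

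**Step 2: is the table read correctly?** The Observer row does not match the text of 4.a, so a shifted row is possible in principle. The PROMIS rows, however, line up with AUDIT-C and DAST-10, which belong on an eligibility form. Their weekly, Week 7 and Week 14 marks agree with 4.a. The text on the Screening televisit mentions anxiety, sleep and gastrointestinal assessments but not mood, and the text on the Treatment televisit mentions only caffeine and cigarette measures. The reading stands.

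**Step 3: which PROMIS scores select participants?** Only PROMIS-Depression appears in a criterion (1 of 5). Inclusion criterion 7 is a choice from a list of problems, and exclusion criterion 4 says anxiety and sleep disorders will not generally exclude.

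**Step 4: size of the drift for PROMIS-Depression.** The plan gives no figure to reproduce on this point. Assumptions, none of them stated for this scale in the documents: normal scores with the same mean and SD on both occasions, everyone above a cutoff c (in SD above the applicant mean) excluded, correlation r between the online and follow-up scores, and no treatment effect.

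- Mean online score of those retained: −φ(c)/Φ(c), in SD units.
- Expected follow-up score: −r × φ(c)/Φ(c).
- Spurious rise: (1 − r) × φ(c)/Φ(c).

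For c = 1: φ = 0.242, Φ = 0.841, ratio 0.288. With r = .5 the rise is 0.5 × 0.288 = 0.144 SD. The value .5 is the repeated-measures correlation that 7.c uses for power, borrowed here.

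| Cutoff c (share excluded, 1 − Φ) | r = .3 | r = .5 | r = .7 | r = .8 |
|---|---|---|---|---|
| 0.5 (31%) | 0.356 | 0.255 | 0.153 | 0.102 |
| 1 (16%) | 0.201 | 0.144 | 0.086 | 0.058 |
| 1.5 (7%) | 0.097 | 0.069 | 0.042 | 0.028 |
| 2 (2%) | 0.039 | 0.028 | 0.017 | 0.011 |

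At r = .5 the drift runs from 0.028 to 0.255 SD. Over the whole grid it runs from 0.011 to 0.356 SD. The direction is always towards worsening.

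**Step 5: what a new baseline would remove.** If the baseline is a second, unselected score taken at the Screening televisit, the drift becomes (r₁ − r₂) × φ(c)/Φ(c). Here r₁ is the correlation of the online score with the new baseline, and r₂ its correlation with follow-up. Equal correlations give zero. With c = 1, r₁ = .7 and r₂ = .5, it is 0.2 × 0.288 = 0.058 SD, against 0.144 SD when the online score is the baseline.

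**The case against.** The best defence is that little is lost. GAD-7, the Pittsburgh index, the Insomnia Severity Index and GSRS are given after consent at the Screening televisit and again at Weeks 7 and 14, so objective (b) keeps a usable baseline for anxiety, sleep and gastrointestinal symptoms. Section 7.b does not list depressed mood; PROMIS-Depression enters through the Table 1 summaries in 7.c. The study is a pilot with a mainly descriptive analysis. All of this stands and limits the harm.

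It can also be said that the word screening in 7.c might cover the online form. That is possible, but 7.b says televisits, and neither section names the form as baseline. The sharp-cutoff model is also simpler than the stated rule, which includes medical history, so the drift figures are only indicative.

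A reader might infer more than the documents support:

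- That PROMIS change is undefined. A pre-treatment value exists and change can be computed from it; what is missing is its designation.
- That all PROMIS baselines are selection scores. This is documented for Depression only. Inflated reporting by applicants on the other four is conjecture.
- That data collected before consent may be unusable. The consent documents are not available here, so this cannot be judged.
- That a planned weekly PROMIS trajectory is compromised. The weekly scores are collected, but no analysis of them is specified.
- That the drift can be set against the partial eta squared of .02. That value belongs to the group-by-time power calculation. Selection before randomisation affects both arms alike in expectation, and the drift is a within-person shift.

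**Conclusion.** The mismatch is certain and needs no assumption: as written, the comparison in 7.b and the pre-treatment summaries in 7.c cannot be produced for any PROMIS scale. The online form is an undesignated substitute of unlimited age. For Anxiety, Sleep Disturbance, GI Diarrhea and GI Reflux the consequence is modest, because parallel scales have a post-consent Screening score.

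For PROMIS-Depression, using the online score as baseline would bias change towards worsening by roughly 0.03 to 0.25 SD at a correlation of .5. That size rests on the assumed cutoffs, normality and a strict cutoff rule; the direction follows from excluding high scorers on the same measurement. The point affects pre-post estimates rather than the randomised comparison, and it merits a cheap improvement, not a redesign.

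**What to change.** In Table 1, add the five PROMIS forms to the Screening televisit, completed after oral consent and before randomisation. In 7.b and 7.c, name that score as the PROMIS screening baseline and state that the online score serves eligibility only. The PROMIS-based exclusion decision should not be re-made on the new score, since that would bring back the same bias. Correct 7.b so that each scale is compared only with visits at which it is given; at present no symptom scale is marked at the Treatment televisit.

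The cost is a few more minutes for participants at one visit budgeted at under 1.5 hours, one change to Table 1 and short edits to 7.b and 7.c. No visit is added.

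The change has limits. Applicants at the Screening televisit have not yet been declared eligible, so any tendency to over-report in order to qualify would remain. In the delayed group the new baseline still precedes treatment by about 7 weeks. The absence of any symptom score at that group's 7-week pre-treatment point is a separate matter that this change does not resolve.
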